13.7 Statistical Monitoring Guidelines

The SC will propose statistical rules for a futility stopping rule (requested by the sponsor) and an efficacy stopping rule at the first DSMC meeting. A decision will be made whether the efficacy stopping rule is appropriate for the study.

14 Chapter 14: Study Team Roles and Responsibilities

- Investigators (UCSF): UCSF will be responsible for study design and implementation, data management and monitoring, data analysis, and dissemination of results. The UCSF investigators will design and implement trainings for study procedures and maintain frequent communication with local Nouna study staff
- Investigators (Nouna): The Nouna investigators will contribute to the study design, implementation, data management and monitoring, data analysis, and dissemination of the results. The Nouna team will oversee all local study activities, including training and regular supervision and monitoring of all local study staff.
- Medical Monitor: The Medical Monitor will provide clinical oversight for the enrolled children. Study team members will report serious adverse events to the Medical Monitor within 24 hours of occurrence. The Medical Monitor will determine if the event is likely to be related to azithromycin and provide clinical guidance for the adverse event as needed.
- Data and Safety Monitoring Committee: The Data and Safety Monitoring Committee will provide independent oversight of data quality and patient safety during the course of the study.
- Study Team Members (Nouna): Study team members in Nouna will be responsible for implementing all study procedures including recruitment, consent, enrollment, randomization, drug administration, and collection of all study data.
 - Hospital Staff: Hospital staff will be trained to determine the randomization allocation of each enrolled child by utilizing the study tablets and administer azithromycin if indicated
 - Outcome Assessor: One outcome assessor will be trained to manage consent, enrollment, and collection of all study data, including outcome assessments

15 Revision History

1/30/19: Addition of [name]

1/31/19: Addition of new inclusion/exclusion criteria (enrollment in NAITRE)

2/1/19: Addition of new Fresh Frozen Stool Protocol, re-formatting, addition of rectal swab risk and fingerstick risk to 11.3.1.

3/11/19: Addition of secondary outcome measure to section 3.5 of malaria. We will measure core body temperature as well as blood smears. Addition of temp to 3.6 participant timeline, chapter 3 baseline information, 7.2 temperature protocol, 11.3 discomfort as risk added

3/14/19: Addition of rectal swab collection in 20 randomly selected children at day 2,4,6,8,10, 12 after treatment. Addition of Chapter 4 to better describe procedures

4/15/19: Change study site information. Will only enroll at Nouna hospital now. Addition of [name]. Section 4.6-Addition of rdt and referral if child has a fever

5/30/19: Rectal swab group no longer has other procedures done. Changes made to section 3.5, 3.6, Chapter 4 Table 1, 4.3, and 6.2.

7/3/19: Removal of the following exclusion criteria:

- Antibiotic use in the past 7 days
- Clinical complications requiring antibiotic treatment
- Clinical complications requiring inpatient treatment
- Congenital abnormality or chronic debilitating illness that would lead to predictable growth faltering or reduce likelihood of treatment benefit (such as cerebral palsy, Down syndrome, congenital heart disease, cleft lip/palate, etc.)

7/19/2019: Rewording for 3.1.1. Removed the word “census” and replaced with “mobilize”

7/29/2019: Changed the sample size for the supplementary rectal swab group from 25 to 50.

Edited Figure 1, Table 1, Sections 3.0, 4.3, and 6.2. Also deleted in section 3.4 the sentence “we will ask about baseline antibiotic consumption.”

8/30/2019: Addition of [name], [name], [name] as authors. Addition of RECTAL primary and secondary outcomes (Section3.5). Addition of RECTAL objective (section 1.2).

9/10/2019: Removal of “home” rectal swabs. Rectal swabs will be collected at home OR at the hospital for the rectal cohort of 50 kids.

10/3/2019: Addition of [name]

11/26/2019: Addition of [name], [name], [name], [name]

3/18/20: Increase sample size (section 1.4, Chapter 3 diagram, 3.2)

3/20/2020: Addition of 6 month window (120-210 days)

2/10/21: Addition of RDT used to section 4.6, addition of 4.8 “Stool” because this section was mistakenly omitted , addition of language to Chapter 7 regarding children unable to produce stool.

7/1/21: Addition of 2 year follow-up timepoint with a rectal swab collection.

16 References

GAMIN II

MORDOR Project

April 9, 2021

Version 1.2

NCT04315272

Statistical Analysis Plan

UCSF Francis I. Proctor Foundation
Centre de Recherche en Santé de Nouna
University of Heidelberg

Introduction

This document (Statistical Analysis Plan, SAP) describes the planned analysis and reporting for the clinical trial, **GAMIN II: Gut and Azithromycin Mechanisms in Infants and Neonates in Burkina Faso**. It includes specifications for the statistical analyses and tables to be prepared for the interim and final Clinical Study Report. This study is a Phase IV clinical trial to compare methods to reduce childhood mortality using mass administration of azithromycin (Pfizer, CAS 83905-01-5) compared to placebo. The content of this Statistical Analysis Plan meets the requirements stated by the US Food and Drug Administration and conforms to the American Statistical Association's Ethical Guidelines.

The following documents were reviewed in preparation of this Statistical Analysis Plan:

- Azithromycin for the reduction of child and infant mortality: Longitudinal Component, Manual of Operations and Procedures
- GAMIN: Gut and Azithromycin Mechanisms in Infants and Neonates in Burkina Faso, Statistical Analysis Plan
- Statistical Analysis Plan, MORDOR Trial
- ICH Guidance on Statistical Principles for Clinical Trials

The planned analyses described in this SAP will be included in future manuscripts. Exploratory analyses not necessarily identified in this Statistical Analysis Plan may be performed to support the analysis. Unplanned analyses not delineated in this Statistical Analysis Plan will be documented as such in the final Clinical Study Report and manuscripts. Note that unplanned analyses will be broadly grouped into two categories:

1. Sensitivity analyses for pre-specified outcomes
2. Other unspecified analyses

Sensitivity analyses are defined as alternate ways of modeling the primary outcome to ensure the finding was not dependent on the analytic plan, and these will not be subject to a multiple comparisons correction. Other unspecified analyses will be declared hypothesis generating or subject to an alpha level of 0.001.

This document will be reviewed prior to the enrollment of patients. All subsequent changes will be indicated by detailed change log in the Appendix.

Contents

1	Summary	5
1.1	Longitudinal Trial	5
2	Statistical Analysis	5
2.1	Planned Analyses	5
2.1.1	Longitudinal Trial	5
3	Sample Size Considerations	6
4	Randomization	7

1.1 Longitudinal Trial

The trial profile is given in the Manual of Operations. In the longitudinal trial, children are randomized to two arms: **Azithro** and **Control**. The trial is a placebo-controlled, double-masked (i.e., double-blind), individual-randomized clinical trial.

Objectives.

Determine the effect of a single dose of azithromycin for children aged 8 days-59 months on rapid diagnostic tests (RDT) for malaria positivity over a 14-day period. Children under 5 years of age will be randomized to a single dose of azithromycin or placebo. *We hypothesize that children randomized to a single dose of azithromycin will have significantly lower RDT positivity after a 14-day period, compared to those randomized to placebo.*

Determine the effect of a single dose of azithromycin for children aged 8 days-59 months on longitudinal changes in the intestinal microbiome over a 6-month period. *We hypothesize that children randomized to a single dose of azithromycin will exhibit a significant difference in the intestinal microbiome after a 6-month period, compared to those randomized to placebo.*

2 Statistical Analysis

2.1 Planned Analyses

2.1.1 Longitudinal Trial

Four hundred fifty children between the ages of 8 days and 59 months may be enrolled in the trial and be offered placebo or azithromycin in a masked fashion. Relevant indicators will be collected using finger prick and fresh frozen stool at days 0, 14, and 180. Children followed up within day 120 and day 240 will be included in primary day 180 analysis.

Primary Analyses. We will compare between arms RDT positivity using logistic regression. We will use permutation tests to estimate coefficient p-values.

We will compare profile of *Campylobacter*, *C. upsaliensis* and *C. hominis* based on L_1 , L_2 distance, and PERMANOVA. We will compare diversity between arms at days 14 and 180 separately, using Shannon's Index and Simpson's Index.

Subgroup analysis. We will restrict the data set to participants RDT negative at baseline and compare between arms RDT positivity at 14-day visit using logistic regression. We will use permutation tests to estimate coefficient p-values.

Statistical considerations.

- Model adequacy will be checked by examination of residuals or other goodness of fit tests as needed. Inadequate model fit will prompt us to report alternative models.
- Multiple imputation will be used in case of missing baseline covariates (if applicable). Missing outcome variables will be handled by sensitivity analysis and reporting of conditional results.
- False Discovery Rate will be calculated for each estimated significant effect.

3 Sample Size Considerations

We assume 80% power to detect a significant effect. We also assume a sample size of 225 per group, no loss to follow-up, and RDT positivity prevalence in the control group of 10%. Given these assumptions, we estimate a detectable effect difference of -0.0659 in proportion of RDT positive participants.

4 Randomization

The randomization will be conducted using R. The function `sample` with option `replace=FALSE` will be used to conduct the random shuffling. Note that the choice of the random number seed completely determines the randomization.

5 Abbreviations

DSMC Data and Safety Monitoring Committee

RDT Rapid Diagnostic Tests for Malaria

SAP Statistical Analysis Plan

6 Revision History

02 Jul 2020 Example revision.

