3.3 Baseline Measurement

After enrollment and informed consent but prior to randomization, baseline samples will be collected. Children will undergo anthropometry (height, weight, mid-upper arm circumference), whole blood venipuncture, a finger prick for malaria blood smears, 2 NP swabs, a rectal swab and they will provide a fresh frozen stool. In addition, study staff will administer a baseline questionnaire inquiring about the child's age and sex as well as the mother's maternal age, education, number of children, and breastfeeding.

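### The SAP's primary diversity comparison leaves out the baseline value of the same index; it is valid but may give up precision, by an amount the documents do not let one state

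*SAP*

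**What the plan says.** SAP 2.1.1 sets two kinds of primary comparison that matter here. For the microbiome: "We will compare diversity between arms at days 14 and 180 separately", on Shannon's and Simpson's indices. For malaria: "We will compare between arms RDT positivity using logistic regression", with permutation p-values. No covariate is named for either.

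Baseline RDT appears only in the subgroup analysis: "We will restrict the data set to participants RDT negative at baseline". The one mention of covariates is conditional and concerns missing data: "Multiple imputation will be used in case of missing baseline covariates (if applicable".

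The SAP Introduction allows other models as sensitivity analyses without a multiplicity correction: "Sensitivity analyses are defined as alternate ways of modeling the primary outcome". It also says "All subsequent changes will be indicated by detailed change log in the Appendix". On allocation, SAP section 4 says that the R function `sample` "will be used to conduct the random shuffling".

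Protocol 3.3 states: "After enrollment and informed consent but prior to randomization, baseline samples will be collected". These include a rectal swab, stool, nasopharyngeal swabs and a finger prick. Protocol 4.11 schedules microbiome sequencing of rectal and nasopharyngeal swabs at days 0, 14 and 180, whereas SAP 2.1.1 mentions finger prick and stool. On the RDT, Protocol 4.6 makes the test conditional on fever, yet the same section counts 407 and 43 children at baseline by kit brand.

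**The concern.** A pre-randomisation measurement of the outcome is usually the first covariate to consider. If it predicts the follow-up value, including it removes variance from the arm comparison without more children and without loss of validity. Here the day-0 value is already scheduled, and the SAP's microbiome objective is framed as change over time, yet the planned comparison uses only the follow-up value.

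The sentence on missing baseline covariates adds doubt, since it leaves open whether any primary model contains one. That choice belongs in the plan, made before anyone sees results by arm. At stake are the width of the interval for the diversity difference and the power of its test.

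**Working it through.** **The plan's own figure.** SAP section 3 gives a detectable RDT difference of -0.0659 with 225 per group, 10% control positivity, 80% power and no loss. Alpha is not stated there; I assume two-sided 0.05. With p1 = 0.10, p2 = 0.0341 and mean 0.06705:

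n = [1.960·√(2·0.06705·0.93295) + 0.842·√(0.09 + 0.0329)]² / 0.0659² = (0.693 + 0.295)² / 0.00434 ≈ 225 per group.

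The figure reproduces and contains no covariate adjustment. The SAP gives no detectable difference for diversity.

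**Diversity.** Adjusting for a baseline value with correlation r multiplies the residual SD, and so the detectable difference, by √(1 − r²). This holds on any index scale and at any sample size. If a share m of baseline values is missing at random and handled by mean plus indicator, the multiplier is √(1 − (1 − m)·r²). The unadjusted sample size giving the same precision is 225/(1 − r²). All values of r and m are my assumptions.

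| r | Multiplier, none missing | Multiplier, 20% missing | Equivalent unadjusted n per arm |
|---|---|---|---|
| 0.2 | 0.980 | 0.984 | 234 |
| 0.3 | 0.954 | 0.963 | 247 |
| 0.5 | 0.866 | 0.894 | 300 |
| 0.7 | 0.714 | 0.780 | 441 |

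As an illustration with the SD of 0.7 in Protocol 3.2, the unadjusted detectable difference at 225 per arm is 2.802 · 0.7 · √(2/225) = 0.185. Adjusted, it is 0.181, 0.176, 0.160 or 0.132. An effect with 80.0% unadjusted power has 81.6%, 83.6%, 89.9% or 97.5% after adjustment.

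**Does a permutation test keep this?** Simulation at 225 per arm, effect 0.264 SD, arm labels permuted and the model refitted:

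| Setting | Unadjusted power | Adjusted power | Adjusted null rejection |
|---|---|---|---|
| r = 0.5, none missing | 79.9% | 89.0% | 4.9% |
| r = 0.5, 20% missing | 78.7% | 85.5% | 5.6% |
| r = 0.7, 20% missing | 78.3% | 96.2% | 4.8% |

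**RDT, only if every child has a baseline RDT.** The kit counts sum to 407 + 43 = 450, the SAP's planned enrolment, but the fever condition in Protocol 4.6 points the other way. Assume 10% baseline positivity and persistence p (the share of baseline-positive controls positive at day 14), with 10% = 0.1·p + 0.9·q fixing q, the day-14 positivity in baseline-negative controls. The relative risk is 0.341 in baseline-negatives. Simulated power at 225 per arm, unadjusted versus stratified score test:

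| p | Same relative risk in baseline-positives | Relative risk 0.7 in baseline-positives |
|---|---|---|
| 20% | 82% v 82% | 69% v 70% |
| 40% | 82% v 84% | 55% v 61% |
| 60% | 82% v 89% | 42% v 55% |
| 80% | 81% v 96% | 30% v 57% |

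In the SAP's logistic model the standard error of the arm log odds ratio rises with adjustment (equal-effect case): 0.45 to 0.52 at 60% persistence and 0.45 to 0.64 at 80%. Power rises because the conditional coefficient lies further from zero. The SD of the risk difference does fall: 0.0220 crude to 0.0203 standardised at 60% persistence.

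**The case against.** The strongest reply is that nothing here is broken. Randomisation makes the unadjusted comparison valid, and the SAP Introduction already permits an adjusted model as a sensitivity analysis. The benefit rests wholly on assumed correlations: at r = 0.2 it is 2% of the detectable difference. A six-month correlation in children enrolled from 8 days of age could be weak. The SAP is dated April 2021 and the day-14 RDTs were done in December 2019, so a late change to a primary model needs care.

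All of that stands, and it limits the point to efficiency. It does not remove it: a permitted sensitivity analysis does not make the primary estimate more precise, and the plan still does not say whether a covariate is in the model.

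Four stronger readings are tempting, and the documents do not support them:

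- *The unadjusted analysis is biased or underpowered.* It is unbiased under randomisation, and no baseline correlation or diversity effect is given from which to call it underpowered.
- *Adjustment would narrow the RDT interval too.* On the log-odds scale it widens, and the odds ratio changes from marginal to conditional on baseline RDT.
- *The RDT test loses dozens of points of power.* The 30% v 57% contrast needs 80% persistence and a weaker effect in baseline-positives. Treated positivity is then 6.3%, not the SAP's 3.41%, so most of the fall from about 82% to 30% is effect dilution. Protocol 4.6 also refers malaria-positive children and lists a different kit at day 14, so persistence may be low.
- *Multiple imputation is wrong here, or analysts have already seen results by arm.* Neither is shown. A single arm-blind rule is only simpler to combine with a permutation test, and masking status at the SAP's date is not stated.

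**Conclusion.** The concern holds for diversity, as a possible loss of precision. SAP 2.1.1 names no baseline value, although one is scheduled from specimens taken before randomisation. The gain runs from near nil to a detectable difference about 29% smaller (r = 0.7), and may be smaller at day 180 than at day 14. It rests on r, which the documents do not give, and shrinks if baseline values are missing.

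For RDT the point is secondary. It applies only if Protocol 4.6 is reconciled in favour of a baseline RDT for all 450 children. The benefit is then in power or in the precision of a standardised risk difference. By the score test it is about nil at 20% persistence.

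**What to change.** Make one logged SAP amendment that states whether the analysts are masked to arm.

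1. **Diversity, each visit and each index:** a linear model with arm and the baseline value of the same index from the same specimen type, which the amendment should name. Obtain the p-value by permuting arm labels and refitting, following the shuffle in SAP section 4 (within blocks if blocks were used).
2. **Missing baseline values:** one arm-blind rule, for example the overall mean plus a missing indicator, held fixed across permutations.
3. **Unadjusted comparison:** keep it as supportive.
4. **If outcomes by arm have already been seen:** keep the unadjusted analysis primary and report the adjusted model as a sensitivity analysis under the SAP Introduction.
5. **RDT:** first reconcile the fever condition with the 407 + 43 children in Protocol 4.6. If baseline RDTs are confirmed for all, add baseline RDT status to the day-14 logistic model, report a standardised risk difference with a named interval method, and say that the odds ratio is conditional. If not confirmed, leave RDT unadjusted and say so.

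The cost is a late amendment and slightly more analysis work. No new data are collected for diversity, nor for RDT if the baseline tests are confirmed.

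### The 80% power at -0.0659 comes from a z-test formula; at the SAP's own design (225 per arm, no loss, arm-only model) the planned permutation test has about 77%

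*SAP*

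**What the plan says.** SAP section 3 is the only power statement in the SAP. It begins "We assume 80% power to detect a significant effect", continues "We also assume a sample size of 225 per group, no loss to follow-up, and RDT positivity prevalence in the control group of 10" percent, and concludes "Given these assumptions, we estimate a detectable effect difference of -0.0659 in proportion of RDT positive participants". No test, alpha level or sidedness is attached to that figure.

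The analysis is in SAP section 2.1.1: "We will compare between arms RDT positivity using logistic regression", followed by "We will use permutation tests to estimate coefficient p-values". No covariate is named for this model. Baseline covariates appear only in a conditional remark about imputing them if there are any.

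SAP section 4 describes allocation by a shuffle without replacement, which fits a permutation test with arm totals held fixed.

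**The concern.** A power figure should describe the test that will be run. A z-test formula treats the difference in proportions as continuous. A permutation test on a binary outcome works with a small set of attainable p-values, and at low event rates it can fall well short of its nominal 5%. If section 3 used the first and section 2.1.1 prescribes the second, the stated 80% is not a property of the planned analysis, even with all 450 children observed. A null result on RDT positivity would then be read as coming from a better-powered comparison than the one performed.

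**Working it through.** **Inputs.** From SAP section 3: n = 225 per arm, no loss, control rate p1 = 0.10, difference -0.0659, so p2 = 0.10 - 0.0659 = 0.0341. From SAP section 2.1.1: logistic regression on arm, permutation p-value. Assumed: two-sided alpha 0.05, arm as the only term, and enough permutations that simulation error is negligible.

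**Step 1: reproduce the plan's figure.** Pooled z-test without continuity correction, with average rate p = (0.10 + 0.0341)/2 = 0.06705:

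power = Φ{[d - 1.960·√(2p(1-p)/n)] / √[(p1(1-p1) + p2(1-p2))/n]}

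= Φ{[0.0659 - 1.960 × 0.02358] / 0.02337} = Φ(0.842) = 80.0%.

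Solving the other way for 80% power gives 0.0659. The alternatives give other detectable differences: unpooled z 0.0656, arcsine 0.0644, continuity-corrected z 0.0695, one-sided 0.05 pooled z 0.0597. This is why the pooled two-sided 0.05 z-test is inferred.

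**Step 2: identify the planned test.** Let s be the total number of positives and x the number in the azithromycin arm. With arm as the only term, the coefficient is log{[x/(225-x)] / [(s-x)/(225-s+x)]}. For fixed s it rises with x and depends on nothing else. Permuting arm labels gives x the hypergeometric distribution, so

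p-value = Σ C(225,x')·C(225,s-x') / C(450,s), over all x' with |x' - s/2| ≥ |x - s/2|.

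Over all 226 × 226 = 51,076 possible outcomes, the rejection region at p ≤ 0.05 matches two-sided Fisher's exact test in every cell.

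**Step 3: why it is conservative.** The expected total under the design alternative is 225 × 0.10 + 225 × 0.0341 = 30.2. With s = 30, a 9 versus 21 split gives p = 0.036 and the next split, 10 versus 20, gives p = 0.088. No attainable value lies nearer to 0.05. With equal arms the two tails tie exactly, so each step adds two outcomes at once.

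**Step 4: power and size, 225 versus 225.** These come from summing binomial probabilities over the rejection region.

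| Quantity | Permutation test | Mid-p version |
|---|---|---|
| Power, 10% vs 3.41% | 76.7% | 81.5% |
| Size, both arms 10% | 3.5% | 4.8% |
| Size, both arms 6.7% | 3.2% | 4.8% |
| Size, both arms 3.41% | 2.6% | 4.4% |

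The permutation test's power is 78.6% at -0.067 and 80.3% at -0.068. Solving for 80% gives -0.0678. Holding the difference at -0.0659 instead, 240 per arm gives 79.8% and 245 gives 80.8%.

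**Step 5: slightly unequal arms.** Same permutation test and rates, with the ordering by absolute coefficient:

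| Control / azithromycin | Power | Size at 10% |
|---|---|---|
| 225 / 225 | 76.7% | 3.5% |
| 224 / 225 | 81.1% | 4.1% |
| 225 / 224 | 76.9% | 4.1% |
| 223 / 227 | 80.2% | 4.2% |
| 227 / 223 | 78.2% | 4.2% |

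The four unequal splits average (81.1 + 76.9 + 80.2 + 78.2)/4 = 79.1%.

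**The case against.** The strongest reply is that 76.7% belongs to one exact split. Removing one child breaks the tie between the tails, and power can rise to 81.1%. This stands: a reader might infer a fixed loss of 3.3 points whatever the data look like, and the unequal splits do not support that. The typical loss is about 1 point. But exactly 225 per group with no loss is the design that section 3 itself assumes, so the stated figure is fairly judged there.

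Second, the match with Fisher's test needs an unadjusted model, and the SAP does not rule covariates out. This also stands as a condition. In an illustrative simulation adjusting for baseline RDT status (assumed: 10% positive at baseline, half of them still positive in the control arm), the permutation test had about 86% power and 4.6% size. No covariate is named, however, so the present text cannot claim that gain.

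Third, the hypothesis is directional ("We hypothesize that children randomized to a single dose of azithromycin will have significantly lower RDT positivity after a 14-day period"), and a one-sided 0.05 permutation test would have 85.5% power. But a one-sided formula gives 0.0597, so section 3 was evidently not calculated that way.

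Fourth, planning with a normal approximation and analysing with a permutation test is common, and moving from -0.0659 to -0.068 is only 0.2 percentage points. That is a fair argument about weight. It does not make the 80% a property of the planned test.

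**Conclusion.** The mismatch is real and modest. Under section 3's own conditions, the test in section 2.1.1 delivers 76.7% power rather than 80%, with 3.5% size at 10% positivity; its detectable difference at 80% power is about -0.068. With near-equal arms, power is about 77% to 81% and size about 4.1% to 4.2%. These figures rest on two-sided 0.05 and the pooled z-test, both inferred because they reproduce -0.0659, and on a model with arm alone.

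Three stronger readings are not supported. The -0.0659 is not an arithmetic slip, since it reproduces exactly from its formula. The planned test is not invalid: it holds its level and errs on the cautious side. And although the same mechanism applies to the subgroup that is RDT negative at baseline, the documents give neither its arm sizes nor its positivity rate, so no size can be quoted for it.

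**What to change.** In SAP section 3, name the test, alpha and sidedness, and restate the figure for the planned test: about 77% power at -0.0659, or 80% at about -0.068, for equal arms and an unadjusted model. This costs one or two sentences, needs no more children and leaves the analysis unchanged.

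The alternative is to keep the 80% claim and specify in SAP section 2.1.1 a mid-p permutation p-value: the proportion of permutations more extreme than the observed one plus half of those tied with it. At the planned rates this gives 81.5% power and 4.8% size. Its cost is the loss of a strict level guarantee, although with 225 per arm the size stayed below 5% at every common rate checked from 1% to 19%.

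Timing matters for this second option. Protocol section 4.6 dates the day 14 visits to December 2019 and the SAP is dated April 2021, so outcomes had already been collected. A change of p-value should be dated in the revision history and made before any comparison by arm is seen; the documents do not say whether one has been. If it has, restating the figure is the safer choice. If the sponsor does intend covariate adjustment, the covariates should be named and the power obtained by simulation.
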